1. OBJECTIVES, SPECIFIC AIMS, BACKGROUND, AND SIGNIFICANCE

Preeclampsia or gestational hypertension—described as hypertension in pregnancy—affects up to 10% of all pregnancies and is a main driver of maternal morbidity in Rhode Island and the United States.¹⁻¹⁴ The rates of hypertension in pregnancy have disproportionately affected women of color and may explain why racial minorities have higher maternal morbidity.^{1,12} The American College of Obstetricians and Gynecologists has called for novel interventions to improve health equity and maternal morbidity outcomes among women hypertension in pregnancy. Technology-based interventions (i.e. remote blood pressure monitoring, telehealth visits, text-based communication) have improved access to care but, to date, have not yet demonstrated an effect on reducing maternal morbidity outcomes.¹⁵⁻¹⁷ It is possible that the lack of effect on maternal morbidity is due to the simplicity of the technology-based interventions previously employed (i.e. text message-based systems). Advanced digital health interventions on blood pressure—namely remote blood pressure monitoring through Bluetooth-enabled blood pressure cuffs and incorporation of a commercially available smartphone application that includes education and patient support as part of a "hypertension in pregnancy pathway"—may more effectively improve perinatal health equity compared to standard SMS-based messaging by reducing perinatal morbidity/mortality among women of color hypertension during their pregnancy. We propose a pilot randomized control trial to examine the feasibility, acceptability, and preliminary estimates of effects of smartphone application-based (app-based) Bluetooth enabled remote blood pressure monitoring (intervention group) when compared to a SMS (short message system such as text message) based remote blood pressure monitoring group (control group). Our long-term goal is to use the most cost-effective intervention (app-based vs SMS-based remote blood pressure monitoring) to improve health equity and maternal morbidity outcomes for pregnant women with hypertension during pregnancy who live in Rhode Island and beyond. We plan to use pilot data from this proposal to support an efficacy trial powered to detect differences in maternal morbidity outcomes between app-based remote blood pressure monitoring and routine care with SMS monitoring.

In addition, this proposal stems from a hospital-wide effort at Women & Infants Hospital (WIH) to reduce racial disparities among women of color in terms of frequency of severe maternal morbidity (SMM). SMM is a metric created by the Centers for Disease Control and Prevention that includes blood transfusion as well as adverse outcomes ranging from arrhythmia to eclampsia to intubation. SMM associated with hypertension is driven by asymptomatic postpartum hypertension. This is easily identified and managed prior to becoming SMM when patients adhere to recommended blood pressure checks after discharge. Excluding blood transfusion (which does not pertain to hypertension), the overall rate of SMM among women with hypertension during pregnancy who deliver at WIH is 6.6%. However, there is a significant difference along racial and ethnic lines: the rate of SMM in the setting of hypertension among black women is 6.8% compared to 4.5% among white women, and the rate of SMM in the setting of preeclampsia is 9.4% among Hispanic women compared to 4.9% among non-Hispanic women. The overall dual aim of the initiative is to reduce the disparity in rates of SMM among those with hypertension between black and white women and between Hispanic and non-Hispanic women by at least 33% by December 31, 2022. As part of WIH's equity initiative, automatic blood pressure cuffs (non Bluetooth enabled) will be provided to all women with hypertension at discharge from delivery hospitalization as part of

routine care. We plan to compare rates of SMM before versus after the hospital-wide implementation of SMS-based remote blood pressure monitoring. Thus, for this proposal, we will build the foundation for our long-term goal and for hospital-wide equity projects by exploring whether app-based remote blood pressure monitoring is required to decrease maternal morbidity compared to standard care with remote SMS blood pressure monitoring.

For this pilot study, sample size limitations will require the use of surrogate markers of maternal morbidity to serve as patient outcomes, which have been selected based on evidence-based best-practices.¹⁻¹⁴ The primary clinical outcome for this study will be blood pressure measurement obtained three to ten days postpartum. Prespecified secondary outcomes include *postpartum readmission for blood pressure management* (e.g. rehospitalizations within 30 days of discharge), *adherence to evidence-based best-practices* (e.g. medications, antepartum surveillance, blood pressure ascertainment, postpartum blood pressure goal of <140/90), *composite severe maternal morbidity* (i.e. stroke, seizure/eclampsia, posterior reversible encephalopathy syndrome, pulmonary edema, heart failure, myocardial infarction, acute fatty liver of pregnancy, hemolysis, elevated liver enzymes and low platelets, placental abruption, post-partum hemorrhage, blood transfusion, acute kidney injury, and transaminitis), *postpartum maternal mortality*, and *composite neonatal morbidity* (i.e. umbilical artery pH <7.10, umbilical artery lactate, seizures, therapeutic hypothermia, hypoxic-ischemic encephalopathy, mechanical ventilation, intrauterine fetal death, neonatal death). We will also explore patient preferences as to treatment group via the Agency for Healthcare Research and Quality Consumer Assessment of Healthcare Providers and Systems (AHRQ CAHPS) survey and compared between both intervention groups and standard prenatal care.²⁵ CAHPS survey will provide mixed quantitative and qualitative assessments. Our *central hypothesis* is that app-based Bluetooth enabled blood pressure monitoring will improve adherence to evidence-based best practices and will demonstrate signals towards improved health equity and maternal morbidity outcomes compared to SMS-based remote blood pressure monitoring.

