Since starting recruitment, an additional challenge has developed: up to 10% of participants in the equity program (who may or may not be in the study) are discharged without blood pressure cuffs with the plan for a home visit to provide a BP cuff within 3-7 days after discharge. In addition, about 10% of patients who participated in the study did not complete their baseline study survey. To ensure we obtain a study population of 120 who follow the study protocol, we have developed an alternative approach by changing our inclusion criteria. Specifically, eligible people may be consented and randomized but only those who receive a BP cuff and complete their intake survey prior to discharge will be included in the trial's analytic population. We anticipate needed to randomize up to 160 patients in order to obtain our desired study population of 120 participants.

2.6 Study outcomes and Power:

Primary outcome: The primary outcomes will be adherence to recommended blood pressure check 3-10 days postpartum, as is recommended per standard of care. Our sample size of **120** pregnant women with gestational hypertension or preeclampsia will allow us to detect a 60% increase in adherence to recommended blood pressure check from the baseline rate of 50%, using a two-tailed alpha of 0.05. The 60% improvement (i.e. from 50% to 80% adherence) is conservative as it is less than has been reported in the medical literature.¹⁵⁻¹⁷ **Secondary outcomes:** Secondary outcomes will be surrogate markers of maternal morbidity.

Prespecified secondary outcomes include postpartum readmission for blood pressure management (e.g. hospital admission for blood pressure management within 30 days of discharge), adherence to evidence-based best-practices (e.g. medications, blood pressure ascertainment, postpartum blood pressure goal of $<140/90$), composite severe maternal morbidity (**Table 2**), and composite neonatal morbidity (Table 1). Our study will likely not be powered to detect differences in secondary outcomes due to the rarity of the individual patient outcomes but will provide us crucial pilot data for the subsequent study.

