2.8 Plan to include a diverse population

Table 2. Composite maternal and neonatal morbidity outcomes

Composite maternal morbidity	
Stroke	
Seizure/eclampsia	
Acute fatty liver of pregnancy	
Posterior reversible encephalopathy syndrome	
Pulmonary edema	
Heart failure	
Hemolysis elevated liver enzymes and low platelets	
Placental abruption	
Post-partum hemorrhage	
Acute kidney injury	
Transaminitis	
Composite neonatal morbidity	
Umbilical artery pH < 7.10	
Umbilical artery lactate	
Seizures	
Therapeutic hypothermia	
Hypoxic-ischemic encephalopathy	
Mechanical ventilation (i.e. intubation)	
Supplemental oxygen 0-6 hours, 6-12 hours, 12-24 hours, >24 hours of life	
Intrauterine fetal death	
Neonatal death	

Inclusion of minorities: This proposal aims to reduce health inequity among women of color with gestational hypertension, preeclampsia, or chronic hypertension. Rates of hypertensive disease in pregnancy are higher among minority women. Given this is our target population, we anticipate that a significant proportion of women included in our study will be minorities. Recruitment will be conducted at prenatal clinics by a research assistant or member of the study team.

Inclusion of fetuses, neonates, and pregnant women: Recent data suggests utilizing remote blood pressure monitoring via text messaging and automatic blood pressure cuffs improves adherence to recommended care.¹⁵⁻¹⁷ As this practice should become standard of care, WIHRI plans to implement SMS-based remote blood pressure monitoring hospital wide for all eligible patients. However, the effect of SMS-based messaging on reducing maternal morbidity outcomes pertaining to hypertension is unknown. In this pilot study, we will compare standard of care (SMS-based remote blood pressure monitoring) to a high quality digital health intervention (smartphone app provided patient education and linked Bluetooth-enabled blood pressure monitoring). This innovative study will allow us to obtain pilot data to determine whether additional digital health support (Bluetooth enabled cuff and app-provided education) is more effective at improve health equity among women of color who deliver at WIH when compared to standard care (SMS-based remote blood pressure monitoring).

3.9 Participant Reimbursement: No reimbursement will be provided for participation, but all participants who complete all required surveys will be entered into a raffle with a prize of \$100

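### The severe maternal morbidity composite counts bleeding events with no time window, and Section 1 adds blood transfusion, which the same section sets aside as unrelated to hypertension

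*Combined protocol and SAP*

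**What the plan says.** Section 1 describes the hospital metric in these words: "SMM is a metric created by the Centers for Disease Control and Prevention that includes blood transfusion as well as adverse outcomes". It then removes transfusion and reports 6.6%: "Excluding blood transfusion (which does not pertain to hypertension), the overall rate of SMM". It attributes hypertension-related morbidity to postpartum hypertension without symptoms, which can be managed if women keep to their checks once they are home.

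The trial's own composite appears in two places.

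- Section 1, in the list of secondary outcomes, includes "placental abruption, post-partum hemorrhage, blood transfusion, acute kidney injury, and transaminitis".
- Section 2.6 (Study outcomes and Power) defines the composite by reference to Table 2. Table 2 (printed under section 2.8) lists "Post-partum hemorrhage" and placental abruption but not blood transfusion. It also lacks myocardial infarction, which the Section 1 list contains.

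Neither place gives a start or an end for counting events. Readmission, by contrast, has a 30-day limit. Sections 2.3 and 2.4 place recruitment in the delivery hospitalization and supply of the cuff at or before discharge. Section 2.7 plans risk ratios and risk differences between arms. Section 1 says the pilot data are to support an efficacy trial powered on maternal morbidity.

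**The concern.** Two separate things look wrong. First, Section 1 gives a reason for leaving transfusion out of a hypertension-related rate and then counts it as a hypertension-related outcome. Table 2 does not, so the protocol carries two composites.

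Second, making the lists agree would not settle the matter, because post-partum hemorrhage is in both. With no time window, a hemorrhage at delivery counts even though the woman has not yet gone home with a cuff. The protocol states no route from home blood pressure monitoring to bleeding. Events that treatment cannot change fall equally on both arms in expectation. They raise both rates and shrink the relative effect.

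At stake is what the pilot passes on. A composite rate and risk ratio made up partly of delivery bleeding would misinform the event rate and effect size used to plan the efficacy trial.

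**Working it through.** **Inputs from the protocol.** Benchmark rate 6.6% (Section 1, transfusion excluded; no counts, period or full component list, so it cannot be recomputed). 60 women per arm (section 2.6). Two-sided alpha 0.05 (section 2.6).

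**Assumptions, not in the protocol.** (i) Bleeding occurs in a proportion b of women, independently of other events and unaffected by treatment. (ii) Hypertension-related events fall by 33% in relative terms. The protocol's 33% is a target for racial and ethnic disparity and is borrowed here only as an example. (iii) The 6.6% stands in for the composite's other components, all of which are treated as modifiable.

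**Events expected in the pilot at 6.6%.** 60 × 0.066 = 3.96 per arm, 7.92 in all.

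**Dilution.** Without bleeding the rates are 0.066 and 0.066 × 0.67 = 0.0442. With bleeding:

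- comparison arm: C0 = 1 − (1 − 0.066)(1 − b)
- intervention arm: C1 = 1 − (1 − 0.0442)(1 − b)
- share of comparison-arm events due to bleeding alone: (C0 − 0.066)/C0
- per-arm size for 80% power: n = [1.96√(2p̄(1 − p̄)) + 0.842√(C0(1 − C0) + C1(1 − C1))]² / (C0 − C1)², with p̄ the mean of C0 and C1

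| b (assumed) | C0 | C1 | Risk ratio | Risk difference | Bleeding-only share | Power, 60 per arm | Total N, 80% power |
|---|---|---|---|---|---|---|---|
| 0 | 6.6% | 4.4% | 0.67 | 2.18 points | 0 | 7.5% | 3,446 |
| 2% | 8.5% | 6.3% | 0.75 | 2.13 points | 22% | 6.5% | 4,722 |
| 5% | 11.3% | 9.2% | 0.82 | 2.07 points | 41% | 5.6% | 6,736 |
| 10% | 15.9% | 14.0% | 0.88 | 1.96 points | 59% | 4.8% | 10,394 |
| 15% | 20.6% | 18.8% | 0.91 | 1.85 points | 68% | 4.4% | 14,480 |

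Worked line, b = 5%: C0 = 1 − 0.934 × 0.95 = 0.1127; C1 = 1 − 0.9558 × 0.95 = 0.0920; ratio 0.816; difference 0.0207.

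**Check with no overlap between event types.** RR = (0.066 × 0.67 + p)/(0.066 + p) gives 0.77, 0.81 and 0.87 for p = 3%, 5% and 10%. The risk difference is then 0.066 × 0.33 = 0.0218 for every p.

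The direction of the shift in the risk ratio holds for any b above zero. The risk difference barely moves, but it is estimated against a higher background rate and so with more variance. That is why the later trial's N rises.

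**The case against.** The strongest reply is that little of this is an error already made, and most of it stands.

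- A reader might infer that the protocol contradicts itself over hemorrhage. It does not. The remark about not being related to hypertension covers transfusion only. That conflict sits in the Section 1 list, since Table 2 already omits transfusion. Doubt about hemorrhage is an inference from timing and mechanism.
- A reader might infer that the trial composite is to be judged against 6.6% or the 33% goal. No such comparison is planned. The before/after comparison belongs to the hospital-wide initiative ("We plan to compare rates of SMM before versus after the hospital-wide implementation of SMS-based remote blood pressure monitoring"), the trial compares randomised arms, and no calculation uses 6.6%.
- A reader might infer that taking bleeding out would make the composite comparable with 6.6%. It would not. The composite includes transaminitis, while arrhythmia and intubation, which Section 1 gives as examples of the hospital metric, are absent from the maternal list.
- Bleeding is not the only doubtful item. Placental abruption also precedes discharge, and other components may. The missing time window is the wider gap.
- The protocol already concedes low power: "Our study will likely not be powered to detect differences in secondary outcomes due to the rarity of the individual patient outcomes". In the table above, power is 4% to 8% whichever definition is used.

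The last point does not dispose of the concern. Outcome definition and event rate are what a pilot hands on, and low power in the pilot does not repair either.

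**Conclusion.** The point holds in a limited form. The inconsistency over transfusion is plain on the text and confined to Section 1. Counting post-partum hemorrhage without a time window is a design weakness, because it admits events that occur before the intervention can act. Its effect is to move the risk ratio toward 1. Under the assumed bleeding rates of 2% to 15%, 0.67 becomes 0.75 to 0.91, the risk difference stays between 1.85 and 2.18 points, and the illustrative efficacy-trial N rises from about 3,446 to between 4,722 and 14,480. These figures show direction and sensitivity only. They depend on a bleeding rate and an effect that the protocol does not give, and on treating all of the 6.6% as modifiable.

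The randomised comparison is not biased by the choice of components, and no inference in this pilot turns on it. The consequence lies in the morbidity estimates meant to support the efficacy trial.

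**What to change.** - Keep one definition of the maternal composite. Take blood transfusion out of the Section 1 list so that it agrees with that section's own reasoning and with Table 2. Settle myocardial infarction, the other difference between the lists, at the same time.
- Report the composite with and without post-partum hemorrhage, and show the bleeding outcomes as separate rows.
- State when counting starts: randomisation or discharge. Recruitment includes triage, labor and delivery, and antepartum units, and the protocol does not say that randomisation always follows delivery. A start at randomisation could therefore still admit some delivery bleeding; a start at discharge would not. State the end of the window too.
- If 6.6% is to inform the next trial, tabulate pilot events under that rate's own definition as well.

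The cost is small. The components are already listed as outcomes, so the separate reporting needs no new ones, though event dates must be available to apply the window. The composite will have fewer events in a comparison already described as underpowered. Section 2.5 shows that recruitment has started, so this is a change to a prespecified outcome and should be dated and documented as an amendment.

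### The primary outcome is worded differently in sections 1 and 2.6: section 1 can be read as a blood pressure value, while the sample size rests only on adherence to the check

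*Combined protocol and SAP*

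**What the plan says.** Section 1 introduces surrogate markers of maternal morbidity as the patient outcomes and then states: "The primary clinical outcome for this study will be blood pressure measurement obtained three to ten days postpartum". It does not say systolic or diastolic, how several readings would be summarised, or what difference is sought. Among the secondary outcomes it lists adherence to best practice, with the examples "e.g. medications, antepartum surveillance, blood pressure ascertainment, postpartum blood pressure goal of <140/90".

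Section 2.6 (Study outcomes and Power) states: "The primary outcomes will be adherence to recommended blood pressure check 3-10 days postpartum, as is recommended per standard of care". The plural is used but only one outcome is named. The sample-size statement concerns that outcome only: 120 women "will allow us to detect a 60% increase in adherence to recommended blood pressure check from the baseline rate of 50" per cent, explained as "from 50% to 80% adherence", "using a two-tailed alpha of 0.05". No power level is given. The secondary list again includes adherence items: "e.g. medications, blood pressure ascertainment, postpartum blood pressure goal of" under 140/90.

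Section 2.7 (Data analysis) gives general tests for continuous and for categorical variables, risk ratios and differences, and logistic regression for adjustment. It does not say which outcome is primary.

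**The concern.** Both statements are in current text, and no sentence says that one stands for the other. On one reading of section 1 the primary is a continuous measurement; in section 2.6 it is a binary process outcome. The two need different tests, rest on different sets of women and have different sample-size requirements, and only the second has any sizing.

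Two things are at stake. First, a primary outcome that the text does not fix leaves room to settle its meaning once data are in hand. Second, the value reading would be a poor primary here. A value in the 3 to 10 day window exists only if a reading was taken, and the trial's hypothesis is that the app changes whether one is taken. Comparing values between arms would therefore compare groups selected after randomisation, at rates the plan itself expects to differ. That fits badly with the intention-to-treat principle stated in sections 2.1 and 2.7.

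The overlap with blood pressure ascertainment adds to the blur: under section 2.6 much the same item appears to be both primary and secondary.

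**Working it through.** **Inputs from the documents.** Adherence 50% and 80%, two-sided alpha 0.05, N = 120 (section 2.6); 60 women per group (the CAHPS text in the same section); 1:1 allocation (section 2.4). The documents give no power level, and no SD or target difference for a blood pressure value.

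**1. The plan's own figure, N = 120 for adherence.** Without a stated power it cannot be strictly reproduced. The total required for 50% versus 80%, two-sided 0.05, is:

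| Power | No continuity correction | With correction |
|---|---|---|
| 80% | 78 | 90 |
| 90% | 104 | 116 |
| 95% | 126 | 140 |

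The nearest variant is 90% power with the correction: 58 per arm, 116 in total.

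**2. Power for adherence at 60 per arm.** The mean proportion is (0.5 + 0.8)/2 = 0.65.

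z = [0.30 × √60 − 1.96 × √(2 × 0.65 × 0.35)] / √(0.5 × 0.5 + 0.8 × 0.2)
= [2.324 − 1.322] / 0.640 = 1.56, so power is about 94.1%.

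Fisher's exact test, enumerated over all tables with 60 per arm, gives 91.3%. The claim that 120 women can detect 50% versus 80% is supported for adherence.

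**3. The value reading: who would have a value.** At the planned rates, 0.5 × 60 = 30 and 0.8 × 60 = 48, which is 78 of 120 women.

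**4. The value reading: detectable difference at 80% power.**

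(1.96 + 0.842) × √(1/30 + 1/48) = 2.80 × 0.2327 = 0.65 SD.

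If all 60 per arm were measured: 2.80 × √(2/60) = 0.51 SD.

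In mmHg, with assumed SDs:

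| Assumed SD | 30 vs 48 measured | 60 vs 60 measured |
|---|---|---|
| 10 | 6.5 | 5.1 |
| 15 | 9.8 | 7.7 |
| 20 | 13.0 | 10.2 |

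**5. The text side by side.**

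| Feature | Section 1 | Section 2.6 |
|---|---|---|
| Primary | A measurement obtained on days 3 to 10 | Adherence to the check on days 3 to 10 |
| Type | Continuous or binary, depending on the reading | Binary |
| Sample-size basis | None | 50% to 80%, N = 120 |
| Blood pressure ascertainment | Secondary | Secondary |

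**The case against.** The strongest reply is that the two sentences describe one outcome. A measurement obtained in the window can simply mean that a reading was obtained, and the window is the same in both sections. The context supports this. The rationale in section 1 is that morbidity is averted when patients keep to recommended checks, and the central hypothesis is about adherence. Blood pressure level already appears as a secondary goal, and none of the details that a value-based primary would need are given. The word clinical may only separate this outcome from the feasibility and acceptability aims. Section 2.6 is also the operative section, with its own primary outcome label, rates, alpha and N, and the risk ratios, risk differences and logistic regression in section 2.7 suit a binary outcome.

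Most of this stands, and it limits the point. A reader might infer that the plan has two competing primary endpoints, or that section 1 definitely means the value. The documents support neither: section 1 is ambiguous, and the sized outcome is identifiable. Nor does the secondary listing of blood pressure ascertainment show that section 1 means a value, because section 2.6 carries the same listing while expressly making adherence primary. The general tests in section 2.7 are likewise no sign that a value-based primary is planned.

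What does not fall away is that the literal wording of section 1, in a paragraph about surrogate markers of morbidity, permits the value reading, and nothing in the plan excludes it.

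**Conclusion.** The point holds as an unresolved definition that should be corrected. It does not show that two primaries will be tested, and it does not show that the trial is undersized. For adherence, 60 per arm gives about 91% to 94% power for 50% versus 80%.

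The harm is conditional on section 1 being followed as a value. In that case the comparison would use about 78 of 120 women, selected after randomisation, with 80% power only for about 0.65 SD. These figures assume that the plan's 50% and 80% are realised, that a value exists only where a check was done, and equal variances with a normal approximation. The mmHg figures rest on assumed SDs of 10 to 20, which the documents do not give.

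**What to change.** 1. In section 1, replace the primary-outcome sentence with the section 2.6 outcome, for example: *The single primary outcome is whether the recommended blood pressure check was done on days 3-10 postpartum, yes/no; no recorded check counts as non-adherent.*
2. Use the same definition, in the singular, in section 2.6.
3. Remove blood pressure ascertainment from the secondary lists in both sections, or define how it differs from the primary.
4. Treat any blood pressure value as secondary.

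The new wording should say nothing about which women are analysed. Section 2.5 limits the analytic population to women who received a cuff and completed the intake survey before discharge, with up to 160 randomised to reach 120. Whether that is right is a separate issue, and a phrase such as *all randomised women* here would change it unannounced.

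The cost is a short text amendment, including one explicit coding rule for women with no recorded check. The sample size and data collection stay as they are.
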